7.4.2 Documenting Reasons for Treatment Discontinuation

A subject may discontinue the trial or be withdrawn from the trial for the reasons listed below:

- Adverse event
 - Subject decides to discontinue because of annoyance or discomfort due to a nonserious AE, which is not otherwise determined to be an undue hazard
 - Continuing infusion of the IMP places the subject at undue risk as determined by the investigator (eg, a safety concern that is possibly, probably, or likely related to IMP)
 - Serious adverse event
 - Other potentially IMP-related safety concerns or AEs
- Death
- Lost to follow-up
- Physician decision
- Protocol deviation
- Site terminated by sponsor
- Trial terminated by sponsor
- Withdrawal by subject
- Other

If the subject discontinues the trial due to an AE, the investigator, or other trial personnel, will make every effort to follow the event until it has resolved or stabilized. Follow-up procedures in [Section 7.4.1](#) must be followed.

7.4.3 Withdrawal of Consent or Assent

All subjects have the right to withdraw their consent from further participation in the trial at any time without prejudice. Subjects cannot withdraw consent for use of data already collected as part of the trial, but only for future participation. The investigator can also discontinue a subject's participation in the trial at any time if medically necessary. Unless the subject provides their written withdrawal of consent or there is other written documentation by the investigator confirming the subject's verbal intent to completely withdraw from the trial, subjects should be followed for all protocol-specified evaluations and assessments, if possible.

Complete withdrawal of consent requires a subject's refusal of ALL of the following methods of follow-up:

- Participation in all follow-up procedures specified in the protocol (whether in-clinic, by telephone, or by an in-home visit).
- Participation in a subset of protocol-specified follow-up procedures (by a frequency schedule and method, as agreed by subject and staff).

- Contact of the subject by trial personnel, even if only by telephone, to assess current medical condition, and obtain necessary medical or laboratory reports relevant to the trial's objectives.
- Contact of alternative person(s) who have been designated in source records as being available to discuss the subject's medical condition, even if only by telephone, mail, or e-mail (eg, family, spouse, partner, legal representative, friend, neighbor, or physician).
- Access to medical information from alternative sources (eg, hospital/clinic medical records, referring doctor's notes, public records, dialysis, transplantation, vital registries, or social media sources).

Withdrawal of consent is a critical trial event and, therefore, should be approached with the same degree of importance and care as is used in initially obtaining informed consent. The reasons for a subject's intended withdrawal need to be completely understood, documented, and managed to protect the rights of the subject and the integrity of the trial. A subject may initially express their desire to discontinue IMP administration, which is not equivalent to a complete withdrawal of consent for further participation (see [Section 7.4.1](#)). A subject may, however, indicate that further trial participation is creating a burden on their work, school, or social schedule. Therefore, the investigator should follow the instructions outlined in [Section 7.4.2](#) to determine if the subject can continue participation in the trial if modifications to his/her treatment and/or Schedule of Assessments can be accommodated. Only subjects who withdraw their permission for all of the above methods of follow-up are considered to have completely withdrawn their consent to participate in the trial.

7.4.4 Procedures to Encourage Continued Trial Participation

Not applicable.

7.5 Definition of Subjects Lost to Follow-up

Subjects who cannot be contacted on or before Final Discharge from trial, who do not have a known reason for discontinuation (eg, withdrew consent or AE), and for whom a survival status at the end of the trial cannot be determined will be classified as "lost to follow-up". Survival status can be determined from a variety of sources, either by obtaining acceptable documentation for death (ie, death certificate, medical records, public records, statement by a family member or primary care physician) or acceptable documentation for life (ie, direct contact with the subject, medical records, successful telephone contact with the subject, statement by a family member or primary care physician, or public records).

The site will make 3 documented attempts to contact the subject by telephone and in the event the site is unable to reach the subject by telephone, the site will attempt to contact the subject via certified mail or an alternative similar method, where appropriate, before assigning a “lost to follow-up” status.

If the subject was classified as “lost to follow-up,” “Were you able to contact the subject?,” “Date of contact/Date of final contact attempt,” and “Contact method” will be recorded in the subject’s eCRF.

8 Trial Procedures

The assessments to be conducted during the trial are summarized in [Section 1.3_Schedule_of_Assessments](#).

Every effort will be made to schedule and perform the procedures as closely as possible to the nominal time, giving considerations to appropriate posture conditions, practical restrictions, and the other procedures to be performed at the same time point.

The highest priority procedures will be performed closest to the nominal time. The order of priority for scheduling procedures around a time point is (in descending order of priority):

- dosing
- blood samples
- urine and feces collections for PK assessments
- any other procedures (ECGs will be scheduled before vital signs measurements).

Where activities at a given time point coincide, consideration must be given to ensure that the following order of activities is maintained: ECGs, vital signs, blood draws.

8.1 Efficacy Assessments

Not applicable.

8.2 Pharmacokinetic Assessments

8.2.1 Pharmacokinetic Blood/Plasma Samples

Blood samples will be collected by venipuncture or cannulation at the times indicated in the Schedule of Assessments ([Table 1.3-1](#)) for determination of OPC-61815 free form and OPC-41061 concentrations, total radioactivity, and metabolite profiling and identification. Blood samples will be collected from the contralateral arm to the arm/hand used for dose administration.

Blood samples will be collected in vacutainers containing K2EDTA and processed into plasma. Approximately 1×2 mL blood sample will be collected for total radioactivity in whole blood and approximately 1×5 mL blood sample will be collected for total radioactivity in plasma. Approximately 1×3 mL blood sample will be collected for OPC-61815 free form and OPC-41061 concentrations in plasma. Approximately 1×10 mL blood sample will be collected for metabolite profiling and identification in plasma.

Procedures for collection, processing, and shipping of blood samples will be detailed in a separate document. If any unknown metabolites are detected and further investigation is necessary, a part of the plasma samples will be shipped on dry ice to the sponsor (Otsuka Pharmaceutical Co., Ltd., Tokushima Research Institute) and used for the structure elucidation of unknown metabolites, which will be conducted separately. The investigation of these unknown metabolites will be reported separately, and the report will not be appended to the clinical study report.

The dates and times of blood collections will be documented in the subject's eCRF.

8.2.2 Pharmacokinetic Urine and Feces Samples

Urine will be collected over the time intervals indicated in the Schedule of Assessments ([Table 1.3-1](#)) for determination of total radioactivity and metabolite profiling and identification.

Feces will be collected over the time intervals indicated in the Schedule of Assessments ([Table 1.3-1](#)) for determination of total radioactivity, and, where possible, metabolite profiling and identification. If possible, a single baseline fecal sample will be collected from after Check-in on Day -1 until just prior to dose administration on Day 1.

Procedures for collection, processing, and shipping of urine and fecal collections will be detailed in a separate document. If any unknown metabolites are detected and further investigation is necessary, a part of the urine samples and/or extracted feces samples will be shipped on dry ice to the sponsor (Otsuka Pharmaceutical Co., Ltd., Tokushima Research Institute) and used for the structure elucidation of unknown metabolites, which will be conducted separately. The investigation of these unknown metabolites will be reported separately, and the report will not be appended to the clinical study report.

The start and end dates and times of each urine collection time point interval and the total volume of urine collected in each time point interval will be documented in the subject's eCRF. The start and end dates and times of each fecal collection time point interval and the total weight of the collected fecal samples for each time point interval will be documented in the subject's eCRF.

8.2.3 Analytical Methodology

Plasma concentrations of OPC-61815 free form and OPC-41061 will be determined using a validated analytical procedure. Whole blood, plasma, urine, and feces total radioactivity will be determined with liquid scintillation counting. Profiling and identification of metabolites in plasma, urine, and, where possible, feces will be conducted using standard laboratory procedures.

8.3 Pharmacodynamic Assessments

Not applicable.

8.4 Pharmacogenomic Assessments

Not applicable.

8.5 Biomarker Assessments

Not applicable.

8.6 Future Biospecimen Research Samples

Not applicable.

8.7 Safety Assessments

Details pertaining to the definitions, collection, reporting, and follow-up of AEs are described in [Section 8.8](#).

8.7.1 Clinical Laboratory Assessments

Clinical laboratory samples will be collected at the time points described in the Schedule of Assessments ([Table 1.3-1](#)) to perform the clinical laboratory evaluations described in [Section 10.2](#).

For assessment of hematology and serum chemistry, 7.5 mL of blood will be required at each time point ([Table 1.3-1](#)), and for assessment of serology (Screening only; [Table 1.3-1](#)), 3.5 mL of blood will be required.

Subjects will be asked to provide urine samples for drugs of abuse screen and cotinine test, and will undergo an alcohol breath test at the times indicated in the Schedule of Assessments ([Table 1.3-1](#)). An investigator (or designee) will perform a clinical assessment of all clinical laboratory data.

The dates and times of collections for clinical laboratory evaluations will be documented in the subject's eCRF. The results of the drugs of abuse screen, cotinine test, and alcohol breath test at Screening and/or Check-in will be documented in the subject's eCRF.

8.7.2 Physical Examination

A full physical examination or symptom-directed physical examination will be performed at the time points as specified in the Schedule of Assessments ([Table 1.3-1](#)).

The dates, times, and results of the physical examinations will be documented in the subject's eCRF.

8.7.3 Vital Signs

Supine blood pressure, supine pulse rate, and oral body temperature will be assessed at the times indicated in the Schedule of Assessments ([Table 1.3-1](#)). Vital signs may also be performed at other times if judged to be clinically appropriate or if the ongoing review of the data suggests a more detailed assessment of vital signs is required.

All measurements will be performed singly, and repeated once if outside the relevant clinical reference range.

Subjects must be supine for at least 5 minutes before blood pressure and pulse rate measurements.

The dates, times, and results of the vital sign measurements (supine blood pressure, supine pulse rate, and oral body temperature) will be documented in the subject's eCRF.

8.7.4 Electrocardiogram

Resting 12-lead ECGs will be recorded after the subject has been supine and at rest for at least 5 minutes at the times indicated in the Schedule of Assessments ([Table 1.3-1](#)).

Single 12-lead ECGs will be performed singly, and repeated once if the Investigator deems a repeat is indicated.

Additional 12-lead ECGs may be performed at other times if judged to be clinically appropriate or if the ongoing review of the data suggests a more detailed assessment of ECGs is required. The investigator (or designee) will perform a clinical assessment of each 12-lead ECG.

The dates, times, and results of the 12-lead ECG (PR interval, QRS, QT-interval, and QT interval corrected for heart rate using Fridericia's formula) will be documented in the subject's eCRF.

8.7.5 Suicidality Monitoring

Not applicable.

8.7.6 Other Safety Variables

Weight will be assessed at the times indicated in the Schedule of Assessments ([Table 1.3-1](#)). The date, time, and weight will be documented in the subject's eCRF at each scheduled time point.

8.8 Adverse Events

8.8.1 Definitions

An AE is defined as any untoward medical occurrence in a clinical trial subject administered an IMP and which does not necessarily have a causal relationship with this treatment. Adverse events would not include information recorded as medical history at Screening for pre-planned procedures for which the underlying condition was known and no worsening occurred. An adverse reaction is any untoward and unintended response to an IMP related to any dose administered.

A suspected adverse reaction is any AE for which there is a reasonable possibility that the IMP caused the AE.

Treatment-emergent AEs are defined as AEs with an onset date on or after the start of open-label treatment. In more detail, TEAEs are all AEs which started after start of open-label IMP treatment; or if the event was continuous from pre-IMP treatment and was worsening, serious, IMP-related, or resulted in death, discontinuation, interruption, or reduction of IMP.

An SAE includes any event that results in any of the following outcomes:

- Death.
- Life-threatening; ie, the subject was, in the opinion of the investigator, at immediate risk of death from the event as it occurred. It does not include an event that, had it occurred in a more severe form, might have caused death.
- Persistent or significant incapacity/disability or substantial disruption of the ability to conduct normal life functions.
- Requires inpatient hospitalization or prolongs hospitalization.
 - Hospitalization itself should not be reported as an SAE; whenever possible the reason for the hospitalization should be reported.
 - Hospitalizations or prolonged hospitalizations for social admissions (ie, those required for reasons of convenience or other nonmedical need) are not considered SAEs.
 - Prescheduled hospitalization to address a condition that has existed prior to the signing of the ICF should not be considered an SAE.

- Congenital anomaly/birth defect.
- Other medically significant events that, based upon appropriate medical judgment, may jeopardize the subject and may require medical or surgical intervention to prevent one of the outcomes listed above; eg, allergic bronchospasm requiring intensive treatment in an emergency room or home, blood dyscrasias or convulsions that do not result in hospitalization, or the development of drug dependency or drug abuse.

Nonserious AEs are all AEs that do not meet the criteria for a "serious" AE.

Adverse Events of Special Interest: A noteworthy event for the particular product/IMP or class of products that a sponsor may wish to monitor carefully. All AESIs are to be reported as immediately reportable events (IREs).

Immediately Reportable Event:

- Any SAE.
- Any AE related to occupational exposure.
- Potential serious hepatotoxicity (see [Section 8.8.6](#)).
- Pregnancy in a female partner of a male subject are also defined as IREs. Although this will only occur in a female partner of a male subject, it must be reported on an IRE form and the Pregnancy Surveillance Form(s) to the sponsor. Pregnancy will only be documented on the AE eCRF if there is an abnormality or complication. This includes pregnancy of the partner of the subject.

Clinical Laboratory Test Value Changes: It is the investigator's responsibility to review the results of laboratory tests for each individual subject as they become available. This review will be documented by the investigator's dated signature on the laboratory report. The investigator may repeat the laboratory test or request additional tests to verify the results of the original laboratory tests. If this laboratory value is considered medically relevant (ie, clinically significant) by the investigator (subject is symptomatic, requiring corrective treatment or further evaluation), or if the laboratory value leads to discontinuation, and/or fulfills a seriousness criterion, this is considered an AE.

Severity: Adverse events will be graded on a 3-point scale and reported as indicated on the eCRF. The severity of an adverse experience is defined as follows:

1 = Mild: Discomfort noticed, but no disruption to daily activity.

2 = Moderate: Discomfort sufficient to reduce or affect normal daily activity.

3 = Severe: Inability to work or perform normal daily activity.

IMP Causality: Assessment of causal relationship of an AE to the use of the IMP is defined as follows:

Related: There is a reasonable possibility of a temporal and causal relationship between the IMP and the AE.

Not Related: There is no temporal or causal relationship between the IMP and the AE.

8.8.2 Eliciting and Reporting Adverse Events

The investigator will regularly assess subjects for the occurrence of AEs. To avoid bias in eliciting AEs, subjects should be asked the nonleading question: “How have you felt since your last visit?” Subjects will also be encouraged to spontaneously report AEs occurring at any other time during the trial to the investigator (or designee).

All AEs (serious and nonserious) reported by the subject must be recorded on the source documents and eCRF provided by the sponsor. Adverse event collection will begin after a subject signs the ICF to Final Discharge from the trial.

Medical terminology should be used for AE reporting. Adverse events should be reported as a single unifying diagnosis whenever possible or, in the absence of a unifying diagnosis, as individual signs or symptoms.

In addition, the sponsor must be notified immediately by telephone, fax, or e-mail of any IREs according to the procedure outlined below in [Section 8.8.3](#). Special attention should be paid to recording hospitalization and concomitant medications.

Adverse event, start date, end date (if possible, start date and time, end date and time), seriousness, severity, relationship to trial treatment (IMP Causality), action taken with trial treatment and outcome will be recorded on the source documents and in the eCRF.

8.8.3 Immediately Reportable Events

The investigator must immediately report (within 24 hours), using an IRE form, after he/she or site personnel become aware of any IRE (SAE, AE related to occupational exposure, potential serious hepatotoxicity, or confirmed pregnancy), by e-mail to the sponsor (Otsuka Global Intake: [contact]). The sponsor is responsible for coordinating the reporting of SAEs/IREs in accordance with the European Directive 2001/20/EC.

Patient confidentiality must be protected and contact information such as name, address, telephone number, or any other protected health information as determined by applicable local regulation should be redacted when forwarding Safety Information and supporting documentation.

8.8.4 Medical Device Incidents (Including Malfunctions)

Not applicable.

8.8.5 Adverse Events of Special Interest

Not applicable.

8.8.6 Potential Serious Hepatotoxicity

For a subject who experiences an elevation in AST or ALT that is $\geq 3 \times$ ULN, a total bilirubin level should also be evaluated. If the total bilirubin is $\geq 2 \times$ ULN, complete an IRE form with all values listed and also report as an AE on the eCRF.

8.8.7 Procedure for Breaking the Blind

This trial will not use blinding procedures.

8.8.8 Follow-up of Adverse Events

8.8.8.1 Follow-up of Nonserious Adverse Events

Nonserious AEs that are identified at any time during the trial must be recorded on the AE eCRF with the current status (ongoing or resolved/recovered) noted. All nonserious events (that are not IREs) that are ongoing at the last scheduled contact will be recorded as ongoing on the eCRF. For any AE having been identified throughout the trial, during analysis, additional relevant medical history information may be requested by the sponsor to further ascertain causality (including, but not limited to, information such as risk-related behavior, family history, and occupation).

8.8.8.2 Follow-up of Immediately Reportable Events

This trial requires that subjects be actively monitored for IREs up to 30 days after the IMP is administered.

Immediately reportable events that are **identified or ongoing at the last scheduled contact** must be recorded as such on the AE eCRF page and the IRE form. If updated information (eg, resolved status) on IRE status becomes available after a subject's last scheduled contact (up to last in-clinic visit for the entire trial), this must be reported to the sponsor and recorded on the AE eCRF page and the IRE form, according to the appropriate reporting procedures described in [Section 8.8.3](#).

It is expected that the investigator will provide or arrange appropriate supportive care for the subject and will provide prompt updates on the subject's status to the sponsor. The investigator will follow IREs until the events are:

- resolved,
- stabilized,
- the subject is lost to follow-up, or
- has died.

Resolution means that the subject has returned to the baseline state of health and stabilized means that the investigator does not expect any further improvement or worsening of the subject's condition. The investigator will continue to report any significant follow-up information to the sponsor up to the point the event has resolved or stabilized, or the subject is lost to follow-up, or has died.

Refer to [Section 10.4](#) for additional information regarding the follow-up period for pregnant partners of male subjects.

8.8.8.3 Follow-up and Reporting of Immediately Reportable Events Occurring After Last Scheduled Contact

Any new IREs reported to the investigator which occur after the last scheduled contact and are determined by the investigator to be reasonably associated with the use of the IMP, should be reported to the sponsor according to the procedures outlined in [Section 8.8.3](#). This may include IREs that are captured on follow-up telephone contact or at any other time point after the defined trial period and continue to report any significant follow-up information to the sponsor until the events are resolved or stabilized, or the subject is lost to follow-up or has died.

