4.1 Type/Design of Trial

This will be a Phase I, single-site, open-label, nonrandomized, single IV dose trial in healthy male Japanese subjects.

Potential subjects will be screened to assess their eligibility to enter the trial within 28 days prior to the dose administration. Subjects will be enrolled and admitted into the trial site on Day -1. On Day 1, all subjects will receive a single IV infusion of 16 mg (¹⁴C)-OPC-61815, containing approximately 75.1 μ Ci (2.78 MBq), over 60 minutes (55 to 65 minutes, inclusive) in the fasted state.

It is planned for at least 8 subjects to be dosed to ensure that 6 subjects complete the IV infusion. Up to a maximum of 10 subjects will be dosed in total.

An overview of the trial design is shown in [Figure 1.2-1](#).

Subjects will be confined to the trial site until at least Day 9. Subjects will be discharged from the trial site on Day 9 if the following discharge criteria are met:

- $\geq 90\%$ mass balance recovery, and/or
- < 1% of the total radioactive dose is recovered in combined excreta (urine and feces) in 2 consecutive 24-hour periods.

If these criteria are not met by Day 9, subjects will remain at the trial site until any one of the discharge criterion are met up to a maximum of Day 10 to continue 24-hour blood,

urine, and feces collections for total radioactivity, unless otherwise agreed upon by the sponsor and investigator.

If criteria are not met by Day 10, subjects may be asked to collect 24-hour excreta samples on up to 2 further occasions on a nonresidential basis to allow extrapolation of urinary and fecal excretion. If needed, the 2 additional 24-hour nonresidential collections will start on Days 10 and 11 (to be brought to the trial site at the end of the collection interval on Days 11 and 12, respectively). If on the second occasion the subject has still not met the desired criterion, then the subject will be discharged from the trial, per investigator and sponsor decision.

Final Discharge from trial will be day of discharge from residential treatment period or the day of last outpatient visit if required to attend them based on the discharge criteria. The total duration of trial participation for each subject (from Screening through Final Discharge from trial) is anticipated to be a maximum of approximately 40 days.

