Subjects who practice true abstinence, because of the subject's lifestyle choice (ie, the subject should not become abstinent just for the purpose of trial participation), are exempt from contraceptive requirements. Periodic abstinence (eg, calendar, ovulation, symptothermal, postovulation methods) and withdrawal are not acceptable methods of contraception. If a subject who is abstinent at the time of signing the ICF becomes sexually active they must agree to use contraception as described previously.

For subjects who are exclusively in same-sex relationships, contraceptive requirements do not apply. If a subject who is in a same-sex relationship at the time of signing the ICF becomes engaged in a heterosexual relationship, they must agree to use contraception as described previously.

Before enrolling males in this clinical trial, investigators must review the below information about trial participation as part of the ICF process. The topics should generally include:

- General information
- Informed consent form
- Pregnancy prevention information
- Contraceptives in current use
- Follow-up of a reported pregnancy

Before trial enrollment, males must be advised of the importance of avoiding pregnancy during trial participation and the potential risk factors for an unintentional pregnancy. Subjects must sign the ICF confirming that the above-mentioned risk factors and the consequences were discussed.

Male subjects must be instructed to contact the investigator immediately, during the trial, if their partner suspects that they might be pregnant (eg, missed or late menstrual cycle).

The investigator must immediately notify the sponsor (within 24 hours) of any pregnancy associated with IMP exposure during the trial and for at least 30 days after dose of IMP, and record the event on the IRE form and forward it to the sponsor. The sponsor will forward the Pregnancy Surveillance Form(s) to the investigator for monitoring the outcome of the pregnancy.

The investigator must report to the sponsor, on the Pregnancy Surveillance Form(s), follow-up information regarding the course of the pregnancy, including perinatal and neonatal outcome. Infants will be followed for a minimum of 6 months from the date of birth.

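### Active monitoring for immediately reportable events is required to Day 31, but the last scheduled contact is on Day 9 to 12, leaving 19 to 22 of the 30 days with no scheduled contact or active procedure

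*Protocol*

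**What the plan says.** The duty is in protocol section 8.8.8.2: "This trial requires that subjects be actively monitored for IREs up to 30 days after the IMP is administered". Section 8.8.1 counts any serious adverse event as an IRE, with no causality condition. It also lists adverse events from occupational exposure and potential serious hepatotoxicity, and adds: "Pregnancy in a female partner of a male subject are also defined as IREs".

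The rest of the plan ends earlier:

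- The last column of Table 1.3-1 is Days 11 to 12. Those visits take place only if the excretion criteria were not met by Day 10.
- Section 4.1 places Final Discharge on the day of residential discharge (Day 9 at the earliest) or of the last outpatient visit (Day 12 at the latest). Participation from Screening to that point "is anticipated to be a maximum of approximately 40 days".
- Section 8.8.2 states: "Adverse event collection will begin after a subject signs the ICF to Final Discharge from the trial".

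For the time after the last scheduled contact, section 8.8.8.3 addresses "Any new IREs reported to the investigator which occur after the last scheduled contact and are determined by the investigator to be reasonably associated" with use of the product. It adds: "This may include IREs that are captured on follow-up telephone contact". No day is given for such a call, and the schedule has no row for it. Section 8.8.8.2 limits the entry of updated IRE information to the period "up to last in-clinic visit for the entire trial".

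Section 10.4 requires the investigator to notify the sponsor "of any pregnancy associated with IMP exposure during the trial and for at least 30 days after dose of IMP". The matching instruction to subjects, to contact the investigator about a suspected partner pregnancy, applies only during the trial.

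The SAP repeats the design (section 4) and adds no later contact. Its listings run to study completion or discontinuation (section 8.1). Its definition of a treatment-emergent event has no end date (section 8.6.1).

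**The concern.** The protocol uses the words required and active for a 30-day safety watch, and its schedule then provides no contact in most of those days. A site that followed Table 1.3-1 and section 8.8.2 to the letter would stop asking at Final Discharge and so would not meet section 8.8.8.2.

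The fallback in section 8.8.8.3 is narrower than the duty in two ways. It waits for a report, whereas the duty is to monitor actively. It also admits only events judged reasonably associated with the product, whereas section 8.8.1 makes any serious event reportable. An unrelated serious event on Day 20, say, would be an IRE inside the 30 days and a treatment-emergent event under the SAP definition. Nothing scheduled would find it, and section 8.8.8.3 would not call for it to be reported.

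At stake is the completeness of IRE capture, and through it the planned summary of serious treatment-emergent events (protocol section 9.4.2.1, SAP section 8.6.1). That summary serves the secondary objective, safety and tolerability. Mass balance, pharmacokinetics and metabolite identification are not involved.

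**Working it through.** **Inputs**

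- Single dose on Day 1 (protocol section 1.1).
- Monitoring window: 30 days after dosing (section 8.8.8.2).
- Final Discharge: Day 9 at the earliest, Day 12 at the latest (sections 1.1 and 4.1).
- Screening starts on Day -28 (section 1.1), and there is no Day 0.
- Stated maximum participation: about 40 days (section 4.1).

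**Step 1. Reproduce the plan's own figure.** Day -28 to Day -1 is 28 days and Day 1 to Day 12 is 12 days: 28 + 12 = 40. The stated maximum is therefore the count to a Day 12 end. A Day 31 contact counted as participation would give 28 + 31 = 59. So the 40-day figure confirms that no Day 31 contact is planned.

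**Step 2. End of the required window.** Day 1 + 30 = Day 31.

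**Step 3. Days without a scheduled contact.** Gap = 31 minus the day of Final Discharge. Share = gap / 30.

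| Final Discharge | Gap (days) | Share of the 30 days |
|---|---|---|
| Day 9 | 31 - 9 = 22 | 73% |
| Day 10 | 31 - 10 = 21 | 70% |
| Day 11 | 31 - 11 = 20 | 67% |
| Day 12 | 31 - 12 = 19 | 63% |

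**Step 4. Sensitivity to the counting rule.** If the dosing day were counted as the first of the 30 days, the window would end on Day 30. The gap would then be 30 - 12 = 18 to 30 - 9 = 21 days. The wording of section 8.8.8.2 counts from after dosing, so 19 to 22 is the better reading. The conclusion is the same either way.

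**Step 5. Does another provision fill the gap?**

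- Section 8.8.8.3 is passive and limited to related events, and the telephone contact it mentions is unscheduled.
- The extra follow-up visit in section 7.4.1 is optional and concerns withdrawn subjects, not completers.
- Section 10.4 obliges the investigator to notify, but schedules no contact through which the investigator would learn of a pregnancy.
- The contact attempts and lost-to-follow-up definition in section 7.5 are tied to Final Discharge.

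None of these is active monitoring of completers between Final Discharge and Day 31.

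**The case against.** The strongest reply is that the protocol does foresee contact after discharge. Section 8.8.8.3 mentions telephone follow-up, section 10.4 carries pregnancy notification to at least 30 days, and sections 4.1 and 4.4 define the end of trial by the last contact or contact attempt, not by Final Discharge. This stands to the extent that passive routes exist. A reader might infer that nothing at all operates after discharge, and the documents do not support that. What is missing is a scheduled contact or active procedure.

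A reader might also infer from the limit on updating IRE records that a known IRE is abandoned at the last in-clinic visit of the trial. It is not. That limit concerns entries on the adverse event eCRF page and the IRE form. The same section keeps the investigator following and reporting an identified IRE until it resolves or stabilizes, contact is lost, or the subject dies. The gap is in detecting new events and in the recording cut-off.

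A third inference would be that section 8.8.8.1, which records a nonserious event still open at the last scheduled contact as ongoing, contradicts section 7.4.1, which follows withdrawn subjects' events to resolution or stabilization. These are different rules for different situations, and neither bears on the 30-day IRE duty.

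Two further limits of the point are fair. The SAP does not define study completion, and its cut-off is stated for listings only. Reading it as Final Discharge relies on the completer definition in protocol section 4.5. And a single call cannot detect a silent laboratory abnormality or reliably reveal a conception late in the window.

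Finally, the risk is small. Section 2.5 reports no serious events in three Phase I trials, and potentially drug-related events occurred during or immediately after dosing. That could justify a shorter window, but then sections 8.8.8.2 and 10.4 should state one.

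**Conclusion.** The point holds. The protocol requires active IRE monitoring to Day 31, and for 19 to 22 of those 30 days (63% to 73%) it provides no scheduled contact or active procedure for a completer. The section that covers later new events adds reporting and relatedness conditions that the duty does not contain.

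The size rests on two assumptions: Final Discharge falls on Day 9 to 12 as planned, and the 30 days are counted from the day after dosing. The probability of a missed event cannot be estimated from the documents and is probably low. No primary endpoint is affected. This is a point of minor severity and a cheap improvement. It is not evidence that the safety results would be materially biased.

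**What to change.** 1. **Table 1.3-1:** add one telephone contact on Day 31 for all dosed subjects, except those who refuse all follow-up under section 7.4.3. Ask about IREs, including partner pregnancy.
2. **Section 8.8.2 and the SAP section 8.1 listing cut-off:** extend collection to that contact, for IREs only.
3. **Sections 8.8.8.2 and 8.8.8.3:** define the last scheduled contact for IREs as this call, so that the relatedness condition applies only to events after it. Replace the limit "up to last in-clinic visit for the entire trial" with the last Day 31 contact of the trial.
4. **Section 10.4:** tell subjects to report a suspected partner pregnancy until at least 30 days after dose.

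Keep Final Discharge, the completer definition (section 4.5) and the 40-day figure, which is defined as Screening through Final Discharge. Add one sentence that a safety call follows on Day 31, about 59 days from the start of Screening. If a subject is not reached after the contact attempts described in section 7.5, record the safety call as not completed and leave his completer status unchanged. No added follow-up of nonserious events or repeat laboratory testing is needed for this point.

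The cost is 8 to 10 calls, one schedule row and the text edits above. The end of trial moves to 19 to 22 days after the last subject's Final Discharge, and database lock would be expected to move with it.
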